## 9 Statistical Considerations

All statistical analyses will be performed under the responsibility of the Sponsor's Biostatistics Platform using the SAS® software, Version 9.4 or above.

The SAP core body will be written and peer-reviewed before the initiation of the study. In accordance with the protocol, the SAP core body will describe all analyses to be performed by the Sponsor.

For descriptive purposes, the following statistics will be presented:

**Table 9.1 - Descriptive statistics produced**

Baseline characteristics and follow-up description	Categorical data	Number and percentage of participants
	Continuous data	Mean, standard deviation, quartiles, minimum, and maximum
Safety results	Categorical data	Solicited and biological safety: Number and percentage (95% CIs) of participants Unsolicited: Number and percentage (95% CIs) of participants, and number of events
	Continuous data	At least mean, standard deviation, minimum, and maximum
Immunogenicity results	Categorical data (such as seroconversion)	Number and percentage (95% CIs) of participants
	Continuous data (titer / data)	$\text{Log}_{10}$ : Mean and standard deviation Anti- $\text{Log}_{10}$ (work on $\text{Log}_{10}$ distribution, and anti- $\text{Log}_{10}$ applied): Geometric mean, 95% CI of the geometric mean, quartiles, minimum, and maximum Graphical representation by RCDC

### 9.1 Statistical Hypotheses

No hypotheses will be tested in this study.

### 9.2 Sample Size Determination Based on HAI Data

Assuming a dropout rate of approximately 10%, a total of approximately 630 participants evaluable for immunogenicity is anticipated.

Table 9.2 shows the expected number of evaluable participants in each study group and each age stratum, and the probability that the lower bound of the 95% CI exceeding the threshold defined by Center for Biologics Evaluation and Research (CBER) requirement for seroconversion and percentage of subjects achieving an HAI antibody titer  $\geq 1:40$  (18).

**Table 9.2 - Probability calculation**

Age in Years	Evaluable Number of Participants (Study Group)	Expected Proportion	CBER: Lower Bound of 2-Sided 95% CI Greater Than	Probability (%)
Percent of participants with HAI antibody titer <math>\geq 1:40</math>				
$\geq 18$	270 (Groups 1 or 2)	0.80	70%	96%
18 to $< 65$	135 (Groups 1 or 2)	0.82	70%	88%
$\geq 65$	135 (Groups 1 or 2)	0.72	60%	82%
$\geq 18$	90 (Group 3)	0.85	70%	93%
18 to $< 65$	45 (Group 3)	0.85	70%	< 80%
$\geq 65$	45 (Group 3)	0.80	60%	83%
Percent of participants with seroconversion for antibody				
$\geq 18$	270 (Groups 1 or 2)	0.50	40%	90%
18 to $< 65$	135 (Groups 1 or 2)	0.52	40%	< 80%
$\geq 65$	135 (Groups 1 or 2)	0.42	30%	82%
$\geq 18$	90 (Group 3)	0.55	40%	80%
18 to $< 65$	45 (Group 3)	0.70	40%	97%
$\geq 65$	45 (Group 3)	0.50	30%	< 80%

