**Table 4.1 – Overall design**

Type of design	parallel, multi-center
Phase	I / II
Control method	active comparator (comparator = Panblok H7 (45 µg) unadjuvanted)
Study population	healthy adults 18 years of age and older
Level and method of blinding	modified double-blind
Study intervention assignment method	randomization
Number of participants	Total of 700 participants  Group 1 (Panblok H7 (7.5 µg) + MF59): 150 participants 18 - 64 years of age 150 participants 65 years of age and older Group 2 (Panblok H7 (15 µg) + MF59): 150 participants 18 - 64 years of age 150 participants 65 years of age and older Group 3 (Panblok H7 (45 µg) unadjuvanted): 50 participants 18 - 64 years of age 50 participants 65 years of age and older
Intervention groups	Eligible participants will be randomized in a 3:3:1 ratio and stratified into two age groups (18 - 64 years of age and $\geq$ 65 years of age). The participants will receive 2 doses, administered 21 days apart, by IM route of either Panblok H7 (7.5 µg) + MF59, Panblok H7 (15 µg) + MF59, or Panblok H7 (45 µg) unadjuvanted.
Total duration of study participation	The study duration for each participant will be approximately 13 months.
Countries	United States
Use of an Independent Data Monitoring Committee, Dose Escalation Committee, or similar review group	No

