#### 3.2 Sample Size Determination

Assuming a dropout rate of approximately 10%, a total of approximately 630 participants evaluable for immunogenicity is anticipated.

No study power was calculated for this study. However, examples were given in the table below showing the probability of 2-sided 95% lower being greater than the CBER thresholds (1), if the proportion of participants with HAI antibody titer  $\geq 1:40$  reach a certain proportion; or if the proportion of participants with seroconversion reach a certain proportion.

Table 3.1 shows the expected number of evaluable participants in each study group and each age stratum, and the probability that the lower bound of the 95% CI exceeding the threshold defined by Center for Biologics Evaluation and Research (CBER) requirement for seroconversion and percentage of participants achieving an HAI antibody titer  $\geq 1:40$  (1).

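### Do the pooled and age-stratum proportions in protocol Table 9.2 and SAP Table 3.1 contradict each other?

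*Protocol*

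**What the plan says.** Protocol section 9.2 assumes about 10% dropout, leaving roughly 630 evaluable of 700. It then introduces the table without calling it illustrative: "Table 9.2 shows the expected number of evaluable participants in each study group and each age stratum", together with the probability of exceeding the CBER threshold.

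The age split is equal by design. For each adjuvanted group, Table 4.1 plans "150 participants 18 - 64 years of age 150 participants 65 years of age and older"; Group 3 has 50 and 50. After 10% dropout that gives 135 + 135 = 270 and 45 + 45 = 90, the evaluable numbers in Table 9.2.

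For HAI titer at or above 1:40 in Groups 1 or 2, the pooled row is "270 (Groups 1 or 2) 0.80 70% 96", the 18 to 64 row is "135 (Groups 1 or 2) 0.82 70% 88" and the 65-and-over row is "135 (Groups 1 or 2) 0.72 60% 82". For seroconversion, the pooled rows are "270 (Groups 1 or 2) 0.50 40% 90" and, for Group 3, "90 (Group 3) 0.55 40% 80".

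The SAP prints the same twelve rows but frames them differently. Section 3.2 states "No study power was calculated for this study. However, examples were given in the table below", and the title of SAP Table 3.1 makes each probability conditional on a given proportion being reached.

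**The concern.** Both tables head the column as an expected proportion, and the evaluable counts add up exactly across strata, so the natural first reading is a single set of expectations for one population. On that reading the pooled and stratum rows cannot both be true. Three pooled values are too high and one is too low, by 0.025 to 0.05, which is more than two-decimal rounding can explain. The table is the only quantitative support in the sample-size section. A reader could therefore ask whether an adjuvanted group's chance of clearing the pooled HAI threshold is 96% or nearer 69%.

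**Working it through.** **Inputs.** Evaluable numbers, proportions and thresholds come from protocol Table 9.2. The equal strata come from Table 4.1. The Clopper-Pearson interval for single proportions comes from section 9.4.2.

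**Step 1: reproduce the printed probabilities.** For each row, find the smallest count r whose Clopper-Pearson two-sided 95% lower bound exceeds the threshold, then compute P(X ≥ r) for X ~ Binomial(n, p).

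| Row | n | p | Threshold | r | Computed | Printed |
|---|---|---|---|---|---|---|
| HAI, Groups 1 or 2, all | 270 | 0.80 | 70% | 205 | 95.7% | 96% |
| HAI, Groups 1 or 2, 18–64 | 135 | 0.82 | 70% | 106 | 87.7% | 88% |
| HAI, Groups 1 or 2, ≥65 | 135 | 0.72 | 60% | 93 | 81.7% | 82% |
| HAI, Group 3, all | 90 | 0.85 | 70% | 72 | 92.6% | 93% |
| HAI, Group 3, 18–64 | 45 | 0.85 | 70% | 38 | 63.9% | below 80% |
| HAI, Group 3, ≥65 | 45 | 0.80 | 60% | 34 | 82.6% | 83% |
| Seroconversion, Groups 1 or 2, all | 270 | 0.50 | 40% | 125 | 89.9% | 90% |
| Seroconversion, Groups 1 or 2, 18–64 | 135 | 0.52 | 40% | 66 | 79.1% | below 80% |
| Seroconversion, Groups 1 or 2, ≥65 | 135 | 0.42 | 30% | 52 | 81.7% | 82% |
| Seroconversion, Group 3, all | 90 | 0.55 | 40% | 46 | 80.2% | 80% |
| Seroconversion, Group 3, 18–64 | 45 | 0.70 | 40% | 26 | 97.2% | 97% |
| Seroconversion, Group 3, ≥65 | 45 | 0.50 | 30% | 21 | 72.4% | below 80% |

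All twelve agree.

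**Step 2: test the one-scenario reading.** With equal strata, the pooled p is (younger p + older p)/2. The share aged 18–64 needed to reach the printed pooled value is (pooled − older)/(younger − older). The mixture probability is P(X₁ + X₂ ≥ r), with independent binomials in the two strata.

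| Pooled row | Printed p | Stratum mean | Share aged 18–64 needed | Printed | Mixture |
|---|---|---|---|---|---|
| HAI, Groups 1 or 2 | 0.80 | (0.82 + 0.72)/2 = 0.77 | 0.08/0.10 = 80% | 96% | 69.3% |
| HAI, Group 3 | 0.85 | (0.85 + 0.80)/2 = 0.825 | 0.05/0.05 = 100% | 93% | 78.1% |
| Seroconversion, Groups 1 or 2 | 0.50 | (0.52 + 0.42)/2 = 0.47 | 0.08/0.10 = 80% | 90% | 61.5% |
| Seroconversion, Group 3 | 0.55 | (0.70 + 0.50)/2 = 0.60 | 0.05/0.20 = 25% | 80% | 96.8% |

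Uneven dropout does not close the gap. A share of 80% of 270 is 216 younger participants, but 150 are randomised per group. Over every attainable mix (150 + 120 to 120 + 150, and 50 + 40 to 40 + 50) the mixture probabilities run 61–77%, 76–80%, 54–68% and 95–98%. None reaches its printed value. Group 3 would also need two different age mixes for two endpoints in the same people. The rows were therefore not built as a mixture.

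**Step 3: see how the rows were built.** Subtract the threshold from the proportion.

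- n = 270: 80 − 70 = 10 and 50 − 40 = 10 points.
- n = 135: 82 − 70, 72 − 60, 52 − 40 and 42 − 30, all 12 points.
- n = 90: 85 − 70 = 15 and 55 − 40 = 15 points.
- n = 45: 15, 20, 30 and 20 points.

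All eight rows with n of 90 or more sit a fixed margin above their threshold, and the margin depends only on n. That is the pattern of a table showing how far above the threshold the true proportion must lie for a good chance of clearing it. On that construction the pooled value has no reason to average the strata.

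**Step 4: test the literal expectation against the rest of the protocol.** Read literally, unadjuvanted Group 3 would outperform the adjuvanted groups in every matching row: 0.85 against 0.80, 0.85 against 0.82, 0.80 against 0.72, 0.55 against 0.50, 0.70 against 0.52 and 0.50 against 0.42. Section 4.3 anticipates stronger responses with adjuvant. The H5 study PSC22 summarised in section 2.2 found 16.7% to 31.5% at HAI 40 or above without adjuvant (45 and 135 µg) and 66% to 81.5% with it. The proportions are not forecasts of this trial's results.

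**The case for a change.** The best case for acting is that the protocol never says this. Section 9.2 sits under a sample-size heading and carries no word such as example. The column is labelled as expected in both documents, and neither states that the pooled and stratum rows are separate scenarios. The pooled rows also correspond to an analysis that will be produced, since section 9.4.2 reports by study group as well as by age stratum. A reader with the protocol alone could reasonably take the 96% as the chance implied by the 0.82 and 0.72 below it, and on those inputs it would be 69%.

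The arithmetic in that argument stands, and so does the complaint about the heading. The inference that the printed probabilities are wrong does not. Each is correct for the condition beside it, and the SAP, to which section 9.4 refers for technical detail, states that the conditions are examples. Replacing the pooled rows with stratum means would impose a joint scenario that neither document adopts, with no firm basis for choosing which rows to keep.

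**Conclusion.** The mismatch is real if the rows are read as one scenario: pooled proportions differ from the stratum means by 0.025 to 0.05, and the pooled probabilities would move to 69%, 78%, 62% and 97%. The SAP wording, the fixed margins and the ordering of Group 3 all point instead to separate illustrations, under which all twelve probabilities are right.

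Nothing in the trial depends on the choice. No hypothesis is tested (protocol 9.1, SAP 3.1). The 630 evaluable is simply 700 × 0.90 and is not solved from these rows. Dose selection uses observed results (protocol 9.5), and results are interpreted against age-specific thresholds (protocol 9.4.2), whereas the pooled rows use the 70% and 40% printed for the younger stratum.

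What is left is a loose column heading and a caveat present in the SAP but absent from protocol 9.2. Tidying either would alter no estimate, interval or decision, so no change is called for. This rests on reading the protocol and SAP together. The documents do not say outright how the proportions were chosen; the margin pattern is an inference from the printed numbers.

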### **Study PSC25**

PSC25 study was a Phase I/II randomized, observer-blind, multi-center study to assess the immunogenicity and safety of 2 doses of Panblok H5 at 3 dose levels of rHA (3.8, 7.5 and 15  $\mu$ g) with a stable oil-in-water emulsion (SE) adjuvant compared to an unadjuvanted Panblok H5 (7.5  $\mu$ g rHA) to select the optimal dose level of rHA to carry forward for future adjuvanted Panblok H5 vaccine development (11).

The rHA in Panblok H5 was derived from A/Indonesia/5/05 (H5N1) influenza virus strain. Panblok H5 was diluted in normal saline to the concentration appropriate for the assigned dose level and administered either as rHA alone (ie, unadjuvanted) or formulated at the study sites with SE adjuvant prior to administration. Two doses, 21 days apart, were administered by IM route in 341 healthy adults 18 to < 50 years of age.

Data from PSC25 study showed that adjuvanted and unadjuvanted Panblok H5 had an acceptable safety profile. Solicited local injection site pain and tenderness were more frequent in the adjuvanted Panblok H5 groups compared to unadjuvanted Panblok H5 group after both doses. Unsolicited AEs from D0 to D42 were similar in frequency and relationship to vaccine across all groups. The incidence of SAEs was < 1% overall, and none were considered to be related to study vaccines.

All dose levels of SE-adjuvanted Panblok H5 met FDA regulatory guidance for licensure criterion for seroconversion (ie, lower bound of the two-sided 95% CI should be  $\geq$  40%) after 2 doses at D42. However, FDA criterion for post-immunization titer  $\geq$  1:40 (ie, lower bound of the two-sided 95% CI should be  $\geq$  70%) was met by the adjuvanted 15  $\mu$ g dose group only. No vaccine groups met any criteria for licensure after a single dose of vaccine.

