## 4.3 Justification for Dose

The 7.5 µg and 15 µg doses were selected based on data from Study BARDA BP-I-17-002 in which these 2 doses showed an immunogenic response without any safety issue. The addition of adjuvant is expected to increase antibody responses, but the dose-sparing potential of the adjuvant will be assessed by using age-matched control groups of unadjuvanted vaccine (ie, Group 3).

Based on data from previous clinical studies and given that most participants will be naïve in the case of a novel pandemic influenza strain, a dose schedule requiring 2 vaccinations, 21 days apart, will be evaluated in the study.

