#### 9.4.2 Primary Endpoints

##### Primary Immunogenicity Objective:

The immunogenicity parameters will be calculated with their 95% CIs using the exact binomial distribution (Clopper-Pearson method) for proportions and using normal approximation of log-transformed for GMTs and GMTs ratio. The 95% CI of proportions difference (ie, difference between vaccine groups in seroconversion) will be calculated using Wilson Score method without continuity correction ([19](#)). All analyses will be conducted by study group and also by age stratum.

The time windows used for collecting blood samples are: D01, D22 [+7], D43 [+7], D202 [+14], and D387 [+14]. To avoid redundancy and typing errors, these time windows will not be reported in all sections of this document.

- Immunogenicity by HIH measurement method
  - GMTs of HAI Ab titers obtained on D22, and on D43 for comparison with D01, D202, and D387.
  - Geometric mean of individual ratios of HAI Ab titers D22/D01 and D43/D01; and D202/D01 and D387/D01.
  - Percent of participants with seroconversion defined as HAI Ab titer < 10 (1/dilution [1/dil]) on D01 and post-injection titer  $\geq$  40 (1/dil) on D22 or D43; or defined as HAI Ab titer  $\geq$  10 (1/dil) on D01 and a  $\geq$  4-fold increase in titer (1/dil) on D22 or D43.  
The interpretation of the results will account for seroconversion thresholds reported in FDA guideline ([18](#)) for participants 18 – 64 years and  $\geq$  65 years of age.
  - Percent of participants with HAI Ab titers  $\geq$  40 (1/dil) on D22, and percent of participants with HAI Ab titers  $\geq$  40 (1/dil) on D43. The same statistic will be calculated for D01, D202, and D387.  
The interpretation of the results will account for seroconversion thresholds reported in FDA guideline ([18](#)) for participants 18 – 64 years and  $\geq$  65 years of age.
  - Percent of participants with detectable HAI Ab titer with a titer  $\geq$  10 (1/dil) on D01, D22, D43, D202, and D387.
  - Difference and its 95% CI in seroconversion between the 3 study doses (Group 1 - Group 3; Group 2 - Group 3, and Group 2 - Group 1) at D22 and D43.
  - Ratio of GMTs and its 95% CI for: Group1/Group3, Group2/Group3, and Group2/Group1 at D22, and at D43.

- The RCDCs of pre-vaccination titer prior to the first vaccination (D01), and post-vaccination titer at D22, D43, D202, and D387 will be generated for each study dose. The RCDCs will include the plots of the 3 doses on the same figure.

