### **9.5 Interim Analyses**

The blind will be broken at the participant level after collecting all immunogenicity and safety data up to 21 days after last vaccination, data are cleaned, and database is locked. The study participants and the laboratory personnel who analyze the blood samples will remain blinded throughout the study. The study team will strive not to communicate the study unblinded data to the sites in order to minimize the bias in collecting the follow-up safety data.

The main analysis of immunogenicity (HIH and SN measurement methods) data and safety will include all data up to 21 days after the last vaccination. The results of this analysis will help in selecting the dose formulation for further clinical development. The results of this main analysis may be reported in an interim clinical study report (CSR).

A final database lock will occur after all data, including up to the 12-month follow-up period, are collected. A final CSR would include the analysis of the safety and immunogenicity data at 6- and 12-month after the last vaccination to assess the persistence of the antibody levels.

No statistical adjustment is necessary because no hypothesis will be tested. Unblinded early looks at the safety data may take place to assess safety.

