### 3.4.2 Primary Endpoints

#### Primary Immunogenicity Objective

The immunogenicity parameters will be calculated with their 95% CIs using the exact binomial distribution (Clopper-Pearson method) for proportions and using normal approximation of log-transformed for GMs and GMs ratio. The 95% CI of proportions difference (i.e., difference between vaccine groups in seroconversion) will be calculated using Wilson Score method without continuity correction (3). All analyses will be conducted by study group and by age stratum.

The time windows used for collecting blood samples are: D01, D22 [+7], D43 [+7], D202 [+14], and D387 [+14]. To avoid redundancy and typing errors, these time windows will not be reported in all sections of this document.

- Immunogenicity by HIH measurement method
  - GMTs of HAI Ab titers obtained on D01, D22, D43, D202, and D387
  - Geometric mean of individual ratios of HAI Ab titers D22/D01, D43/D01, D202/D01, D387/D01, D22/D202, D22/D387, D202/D43 and D387/D43
  - Percentage of participants with seroconversion defined as HAI Ab titer < 10 (1/dilution [1/dil]) on D01 and post-injection titer  $\geq$  40 (1/dil) on D43 or defined as titer  $\geq$  10 (1/dil) on D01 and a  $\geq$  4-fold increase in titer (1/dil) on D43.  
Percentage of participants with seroconversion defined as HAI Ab titer < 10 (1/dilution [1/dil]) on D01 and post-injection titer  $\geq$  40 (1/dil) on D22 or defined as titer  $\geq$  10 (1/dil) on D01 and a  $\geq$  4-fold increase in titer (1/dil) on D22.  
The interpretation of the results will account for seroconversion thresholds reported in FDA guideline (1) for participants 18 – 64 years and  $\geq$  65 years of age.
  - Percent of participants with HAI Ab titers  $\geq$  40 (1/dil) on D22, and percent of participants with HAI Ab titers  $\geq$  40 (1/dil) on D43. The same statistic will be calculated for D01, D202, and D387.  
The interpretation of the results will account for sero-protection thresholds reported in FDA guideline (1) for participants 18 – 64 years and  $\geq$  65 years of age.
  - Percent of participants with detectable HAI Ab titer  $\geq$  10 (1/dil) on D01, D22, D43, D202, and D387.
  - Difference and its 95% CI in seroconversion between the 3 study doses (Group 1 - Group 3; Group 2 - Group 3, and Group 2 - Group 1) at D22 and D43.
  - Ratio of GMTs and its 95% CI for: Group1/Group3, Group2/Group3, and Group2/Group1 at D22, and at D43.

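### Does Table 9.2 mask the effect of unequal arm sizes, and is a between-group difference for HAI titre ≥ 40 missing from the plan?

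*Protocol*

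**What the plan says.** Protocol 9.2, Table 9.2 (repeated as SAP Table 3.1) lists, by age stratum and group, an evaluable number, a proportion, a CBER threshold and the probability that the lower limit of the two-sided 95% CI exceeds the threshold. Two of its rows, both for titre ≥ 1:40 at age 65 and over, read "135 (Groups 1 or 2) 0.72 60% 82"% and "45 (Group 3) 0.80 60% 83"%. SAP 3.2 adds that no power was calculated and that the rows are examples. Protocol 9.1 and SAP 3.1 state that no hypotheses are tested.

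Protocol 9.4.2 plans, for the HAI results, "Difference and its 95% CI in seroconversion between the 3 study doses" at D22 and D43, with a Wilson score interval, together with GMT ratios between all pairs of groups. The percentage with titre ≥ 40 is reported per group with an exact CI, and no between-group difference is listed for it.

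On thresholds, the protocol says "The interpretation of the results will account for seroconversion thresholds reported in FDA guideline". For titre ≥ 40 the SAP says "The interpretation of the results will account for sero-protection thresholds reported in FDA guideline". Both refer to the two age strata. On the control arm, protocol 4.3 says "the dose-sparing potential of the adjuvant will be assessed by using age-matched control groups of unadjuvanted vaccine". On the D43 analysis, protocol 9.5 says "The results of this analysis will help in selecting the dose formulation for further clinical development".

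**The concern.** Within every age group and endpoint, Table 9.2 assumes a higher proportion for Group 3 than for Groups 1 or 2, and no proportion appears at both n = 135 and n = 45. A reader who sees 82% beside 83% could think the arms have a similar chance of meeting the criterion. They do not: with the same true proportion, an arm of 45 misses the threshold far more often than an arm of 135.

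That could matter because the primary objective compares each adjuvanted dose with Group 3, because results are to be read with the FDA thresholds in mind, and because the background reports an earlier trial by group status (the titre criterion "was met by the adjuvanted 15" µg group only). If an adjuvanted arm met the bound and Group 3 missed it, the contrast might be read as an effect of the adjuvant when it came only from the 3:1 size ratio. For titre ≥ 40 no difference with a CI is listed to correct that reading.

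**Working it through.** **Inputs.** Evaluable numbers of 135 and 45 per stratum are 150 × 0.9 and 50 × 0.9 (protocol 9.2, 10% dropout). Proportions and thresholds are from Table 9.2. The single-proportion CI is Clopper-Pearson (protocol 9.4.2).

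**Step 1: reproduce the table.** For each row, let k be the smallest count whose Clopper-Pearson lower 95% limit exceeds the threshold. The probability is P(X ≥ k) with X ~ Bin(n, p). For n = 45, p = 0.80 and threshold 60%, k = 34 and P = 82.6% (printed 83%). All rows, in table order:

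| Endpoint | n | p | Threshold | Printed | Recomputed |
|---|---|---|---|---|---|
| Titre | 270 | 0.80 | 70% | 96% | 95.7% |
| Titre | 135 | 0.82 | 70% | 88% | 87.7% |
| Titre | 135 | 0.72 | 60% | 82% | 81.7% |
| Titre | 90 | 0.85 | 70% | 93% | 92.6% |
| Titre | 45 | 0.85 | 70% | < 80% | 63.9% |
| Titre | 45 | 0.80 | 60% | 83% | 82.6% |
| Seroconversion | 270 | 0.50 | 40% | 90% | 89.9% |
| Seroconversion | 135 | 0.52 | 40% | < 80% | 79.1% |
| Seroconversion | 135 | 0.42 | 30% | 82% | 81.7% |
| Seroconversion | 90 | 0.55 | 40% | 80% | 80.2% |
| Seroconversion | 45 | 0.70 | 40% | 97% | 97.2% |
| Seroconversion | 45 | 0.50 | 30% | < 80% | 72.4% |

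All 12 agree.

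**Step 2: size of the arm-size effect.** Assume the same true p in both arms and write a and b for the probabilities of clearing the bound with n = 135 and n = 45. The larger arm meets the bound and the smaller misses it with probability a(1 − b); the reverse is (1 − a)b.

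| Threshold | k/135 | k/45 | p | a | b | a(1 − b) | (1 − a)b |
|---|---|---|---|---|---|---|---|
| 70% | 106 (78.5%) | 38 (84.4%) | 0.82 | 87.7% | 42.4% | 51% | 5% |
| 70% | 106 | 38 | 0.85 | 98.4% | 63.9% | 35% | 1% |
| 60% | 93 (68.9%) | 34 (75.6%) | 0.72 | 81.7% | 36.6% | 52% | 7% |
| 60% | 93 | 34 | 0.80 | 99.9% | 82.6% | 17% | 0.1% |
| 40% | 66 (48.9%) | 26 (57.8%) | 0.52 | 79.1% | 26.6% | 58% | 6% |
| 40% | 66 | 26 | 0.70 | > 99.9% | 97.2% | 3% | < 0.1% |
| 30% | 52 (38.5%) | 21 (46.7%) | 0.42 | 81.7% | 31.2% | 56% | 6% |
| 30% | 52 | 21 | 0.50 | 99.7% | 72.4% | 27% | 0.2% |

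So threshold status does depend strongly on arm size. The frequency of discordant status runs from 3% to 58%, depending on which of the table's own proportions is taken as the common one.

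**Step 3: does the table hide this?** Every row prints its n. The row pairs (Groups 1 or 2, then Group 3) print 96 and 93, 88 and < 80, 82 and 83, 90 and 80, < 80 and 97, 82 and < 80. In four of the six, Group 3 has the higher proportion and the lower probability. The table also shows one proportion against one threshold at two sizes: 0.85 against 70% gives 93% at n = 90 and < 80% at n = 45.

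**Step 4: is titre ≥ 40 left without a comparison?** Under the planned definition, a participant with D01 titre below 10 seroconverts exactly when the later titre is ≥ 40. With D01 titre ≥ 10, a 4-fold rise gives at least 4 × 10 = 40. Seroconversion therefore always implies titre ≥ 40, and the two can differ only in participants with D01 titre ≥ 10. If that share is at most s in each arm, then in each arm

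0 ≤ P(titre ≥ 40) − P(seroconversion) ≤ s,

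and the two between-arm differences cannot be more than s apart. The documents give no value for s, but SAP Table 1.1 describes naive participants, protocol 4.2 expects most to be naive, and exclusion E09 removes earlier investigational H7N9 vaccination. The percentage with D01 titre ≥ 10 is itself a planned output, so s will be known for each arm.

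**The case for a change.** The strongest case for a change is this. An observed 80% at age 18-64 meets the 70% bound with 108/135 (lower limit 72.3%) and misses it with 36/45 (65.4%). A Wilson score difference would show 0 points (95% CI −11.8 to +15.0) instead of one arm meeting the criterion and the other not. The method is already in the plan, the line costs almost nothing, and titre ≥ 40 is one of the two endpoints in the sample-size table. Table 9.2 also assigns different proportions to the two endpoints (0.82 and 0.52, 0.72 and 0.42), which suggests that one does not stand in for the other.

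The arithmetic stands, and so does the fact that no such line is listed. The rest is weaker:

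- No document says status will be compared between arms. The thresholds are bounds on each group's own CI, and the planned comparisons are differences and ratios.
- Under equal true proportions, 7.5 or 15 µg with MF59 would be doing as well as 45 µg without it. Concluding that antigen is spared would then be correct. Only a claim of superiority over 45 µg would be false, and none is planned on the basis of threshold status.
- The choice between the two adjuvanted doses is unaffected, since those arms are equal in size.
- The table's proportions are not joint predictions. For Groups 1 or 2 they lie 10 or 12 points above the threshold in every row (0.80 − 0.70, 0.82 − 0.70, 0.72 − 0.60, 0.50 − 0.40, 0.52 − 0.40, 0.42 − 0.30). A 30-point gap between the endpoints would require at least 30% of participants to have a D01 titre ≥ 10, which does not fit a mostly naive population.

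**Conclusion.** No change to the plan is needed. Table 9.2 is correct in all 12 rows, its inputs are illustrative by the SAP's own account, and it lets a reader see what a smaller arm costs. Comparing threshold status across arms of 135 and 45 would mislead, with discordant status in 3% to 58% of trials at equal true proportions, but neither document plans that comparison.

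The absent difference for titre ≥ 40 is a small gap that analysts can fill without loss. Counts and exact CIs are planned for each group, so the difference can be computed from the reported tables. The planned seroconversion difference tracks it to within the share with D01 titre ≥ 10. GMT ratios and reverse cumulative curves with all three doses on one figure complete the comparison. Listing the line explicitly is a reasonable option, but it is not expected to alter a conclusion. Printing exact values for the < 80% cells or renaming the column would correct no error.

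This rests on two things: the trial stays descriptive, as both documents say, and the enrolled population is mostly naive to H7, which the planned D01 results will show.
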